3.4 Primary Safety Endpoints

Safety measures

- Adverse events
- Laboratory values
 CBC

 - Metabolic panel
- Urinalysis
- Vital signs
- Body temperature
- Weight
- Blood pressure (sitting and standing)
- ECG (at screening and termination visit)

Tolerability measures

- Number of subjects (%) who discontinue the study
- Number of subjects (%) who discontinue the study due to AEs.
- Severity of hypotension during an active stand test
- Lowest systolic BP (24-h)
- Worsening in OH-Q scores
- Frequency of symptoms noted in their diary

4 Subject Selection and Withdrawal

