Symptom Diary: As we did in our previous trial, ¹³ we will use a tailored questionnaire to examine symptoms over the treatment period and the used of as needed medications. Each day will have a designated page. Since nausea/vomiting and hypertension occur together in FD we will use a diary consisting of a simplified version of the Rhodes Index ⁴⁴ symptoms of nausea/retching, with items addressing vomiting/throwing up omitted, as most participants will have had anti-reflux surgery to prevent vomiting (fundoplication), graded on a 5-point scale (appendix 2). The diary will also include space to write down any adverse events on a daily basis.

Catecholamines:

Prior to arriving for a study visit or performing a televisit, patients will be asked to collect a 24-hour urine sample in a bottle shielded from light containing preservative. Patients will be instructed to refrigerate their sample and bring it on the morning of their visit in a cool bag or provided with a prescription to take it to a local laboratory. Catecholamines will be measured using high-pressure liquid chromatography as previously described. 45 Because urine catecholamine collections reflect periods of sympathetic nerve activation over an entire day, in this particular circumstance urinary excretion will more clinically useful information, than a plasma "snap-shot" obtained from a blood draw at the office, which has the emotional component of a having and IV inserted in the arm (which despite not feeling pain, is not well tolerated by these patients).

Autonomic Testing:

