7.2 Statistical Methods

We have a dedicated statistician for this clinical trial ([name], PhD). Our inclusion criteria use a baseline SD of systolic blood pressure variability ≥15 mmHg (2 SD above our age-matched control data [8.7±3 mmHg]). The mean coefficient of variation in 24-h BP readings in patients with FD is 19.1±5 and 99% of FD patients meet the inclusion criteria. Preliminary data shows that treatment with high dose carbidopa (600 mg/day) reduces blood pressure variability (SD of daytime SBP) by 7.0±5.5 mmHg. Power analysis for the primary outcome (reduction in SD of daytime SBP variability) is detailed in table 3. A sample size of 20 achieves 80% power to detect a reduction of 2.5 (or 2.9) from the null hypothesis of no reduction with an estimated standard deviation of 4.4 for the difference in SD at a significance level of 0.05 using a one-sided (or two-sided) one-sample t-test. The minimum detectable differences are all well below the observed reduction of BP fluctuation of 5.1 from our preliminary data. To ensure that the study is well powered, we will choose a sample size of 30 patients. To account for a drop out rate of around 15%, we will enroll 36 patients in the trial. We will examine the sample distribution of SD of daytime SBP, and if it deviates from the normal distribution, we will employ the nonparametric Wilcoxon test for robustness. In addition, to account for potential covariates, such as age, gender, and disease severity, the analysis of (co)variance (ANOVA and ANCOVA) methods will be used to model the repeated measures data.

Table 3: Power Calculation and Sample Size

Minimal detectable difference: SD BP variability high vs. low dose							
Sample size	T-test	T-test					
	One-sided	Two-sided					
20	-2.5	-2.9					
30	-2.0	-2.3					
40	-1.8	-2.0					

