We are interested in how the low blood pressure symptoms that you experiences affect daily life. Please rate each item by ticking the number that best represents how much on the average the activity has been interfered with over the past week by the low blood pressure symptoms you have experienced. If you cannot do the activity for reasons other than low blood pressure, please check the box at right.									
			☐ Cannot do for other						
1. Activities that red	quire standing f	or a short time	reasons						
No 0	No 0 1 2 3 4 5 6 7 8 9 10 Complete								
interference			│						
	☐ Cannot do for other								
2. Activities that red	quire standing for	or a long time	2. Activities that require standing for a long time reasons						
	1 2 3								
	1 2 3								
No 0	1 2 3		9 10 Complete						
No 0 interference	1 2 3		9 10 Complete						
No 0 interference		4 5 6 7 8	9 10 Complete interference						
No 0 interference		4 5 6 7 8	9 10 Complete interference Cannot do for other reasons						
No 0 interference 3. Activities that red	quire walking fo	r a short time	9 10 Complete interference Cannot do for other reasons						
No 0 interference 3. Activities that rec	quire walking fo	r a short time	9 10 Complete interference Cannot do for other reasons 9 10 Complete						
No 0 interference 3. Activities that rec	quire walking fo	r a short time	9 10 Complete interference Cannot do for other reasons 9 10 Complete						
No 0 interference 3. Activities that rec	quire walking fo	r a short time 4	9 10 Complete interference Cannot do for other reasons 9 10 Complete interference						
No 0 interference	quire walking fo	r a short time 4	9 10 Complete interference Cannot do for other reasons 9 10 Complete interference Cannot do for other						

SYMPTOM DIAR	Y					
Name (last, first	t):					
Current dat	-		Time:			
Retching is the effor Please mark the bo Please make only o	x in each rov	w that most o		ponds to you	ır experience	-
In the last 24 hours, I have felt nauseated or sick to my stomach	Not at all	1-hour or less	2-3 hours	4-6 hours	More than 6 hours	
In the last 24 hours, from nausea/sickness, I have felt "" distress	No	Mild	Moderate	Great	Severe	
In the last 24 hours, I have had periods of retching.	No	1 – 2 hours	3 – 4 hours	5 – 6 hours	7 or more	
What time of day was the worst?						
Did you miss school or work?	□ No □ Yes					
Did you take something for your nausea today?	□ No □ Yes	 3				
Did you take something for your blood pressure today?	□ No □ Yes					

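### The diary's retching row asks about periods but answers in hours and has no box for retching under one hour, so short retching is recorded as absent or as 1–2 hours

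*Combined protocol and SAP*

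**What the plan says.** Section 3.4 lists six tolerability measures. The last is "Frequency of symptoms noted in their diary". The protocol does not say whether frequency means episodes, days with the symptom, or something else, and gives no scoring rule for the diary.

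Section 6, under Symptom Diary, describes the instrument: "we will use a diary consisting of a simplified version of the Rhodes Index", limited to nausea and retching, with each item graded on five points and one page per day. Vomiting items are left out because most participants will have had anti-reflux surgery. The same paragraph adds: "The diary will also include space to write down any adverse events on a daily basis".

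The form is in the Appendix. Its retching row reads "In the last 24 hours, I have had periods of retching", followed by the boxes No, 1–2 hours, 3–4 hours, 5–6 hours and 7 or more. The nausea-duration row on the same page has the boxes Not at all, 1 hour or less, 2–3 hours, 4–6 hours and More than 6 hours. The instruction above the rows is damaged in the text available, but appears to ask the patient to mark the box in each row that comes closest to the experience.

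**The concern.** A respondent who retched for twenty minutes finds no box that describes the day. The nausea row provides for short episodes, so the form allows for brevity in one symptom and not in the other. The word periods also invites a count, while the boxes ask for hours. If the top box really has no unit, one person may take it as seven bouts and another as seven hours.

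Retching matters more here than its place on the page suggests. With vomiting items removed, nausea and retching are the only symptoms the diary grades. Section 1.4 reports that carbidopa lessened nausea, retching and vomiting episodes in the previous trial, so these data are likely to be examined. Section 4.3.1 estimates that around 40% of patients have impaired cognitive function, and Section 1.6.2 has patients or caregivers keep the diary. An ambiguous row is more likely to be answered inconsistently in that setting.

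**Working it through.** The plan gives no figure to reproduce on this point. The check is whether the boxes cover the possible answers, and what each possible meaning of frequency needs from the row.

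**Coverage, reading every retching box as hours**

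| Time with symptom in 24 h | Retching row | Nausea row |
|---|---|---|
| None | No | Not at all |
| Above 0, below 1 h | no box | 1 hour or less |
| 1 h | 1–2 hours | 1 hour or less |
| 2 h | 1–2 hours | 2–3 hours |
| 3 h | 3–4 hours | 2–3 hours |
| 4 h | 3–4 hours | 4–6 hours |
| 5 or 6 h | 5–6 hours | 4–6 hours |
| 7 h or more | 7 or more | More than 6 hours |

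Both rows place every whole-hour answer, and both leave gaps between whole-hour bands (for example between 2 and 3 hours for retching, and between 1 and 2 hours for nausea). Rounding across those gaps only moves a day between neighbouring non-zero grades. The sub-hour gap in the retching row differs in kind, because it lies on the boundary between symptom present and symptom absent.

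**What a best-match rule does to short retching.** The two nearest boxes are No (0 h) and the lower edge of 1–2 hours (1 h). The midpoint is (0 + 1)/2 = 0.5 h. Retching under about 30 minutes is nearest to No, and retching of 30 to 60 minutes is nearest to 1–2 hours. The first is recorded as no event, and the second is recorded as longer than it was.

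**Consequence under each possible meaning of the Section 3.4 measure**

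- *Days with any retching:* hour bands can supply this, as any answer other than No counts. The error is the loss of short-retching days entered as No. Rounding up, or an ambiguous top box, does no harm to this summary.
- *Number of episodes:* hour bands do not supply it. One bout of 60 minutes and four of 15 minutes (4 × 15 = 60) give the same answer.
- *Grade or duration:* short retching is scored either zero or at the 1–2 hour grade, and the top grade is unclear if its unit is really missing.

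**Exposure.** Scheduled diary pages for the 30 subjects in the Study Summary: 30 × 3 periods × 28 days = 2,520. This is the number of pages that carry the row. It is not a count of errors: days with no retching, or with an hour or more scored in hours, are not touched by the sub-hour gap.

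**Reach.** The row enters one of six tolerability measures. It enters none of the endpoints in Sections 3.2 and 3.3. Section 7.2 bases its calculation on blood pressure: "Power analysis for the primary outcome (reduction in SD of daytime SBP variability) is detailed in table 3".

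**The case against.** The strongest reply is that this is a small defect on a form that still works. A reader might go further than the text allows in four ways, and the reply is right on each.

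- *That short retching has no valid answer.* The instruction, as far as it can be read, asks for the closest box, so every day has one. What stands is that the closest box is inaccurate for sub-hour retching.
- *That the symptom-frequency measure as a whole is mismeasured, or cannot be obtained from hour bands.* Days with any answer other than No is a frequency, and other diary items contribute to the measure. The protocol nowhere defines frequency as bouts. What stands is that the retching component is less accurate and that no definition is given.
- *That the top box certainly lacks a unit.* The surrounding text is visibly damaged, so the unit may have been lost in extraction. The three boxes before it all say hours, which makes hours the natural reading. The sub-hour gap and the mismatch between stem and boxes do not depend on this.
- *That the comparison of treatments is biased.* The same form is used in all three blinded periods and each patient is their own control, so a stable answering habit applies to every treatment. Error could depend on treatment if a treatment shortened bouts to under an hour: rounding down would show retching abolished, and rounding up could hide the improvement. The documents give no bout lengths, so this remains a possibility only.

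Other safeguards also stand. Nausea duration and distress are scored separately, the diary has space for adverse events, and adverse events are sought at weekly calls and by specific questioning (Section 8.2). None of these restores a graded retching record for short bouts.

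**Conclusion.** The point holds as a minor instrument defect. Completed as printed, the row records short retching as absent or as 1–2 hours, and its stem and boxes measure different things. The effect is a coarser and less accurate retching component in one tolerability measure, most plausibly a loss of sensitivity. The size cannot be given: the share of days with retching under one hour is not in the documents, and the 2,520 scheduled pages are only the exposure. No bias between treatments is shown, and the efficacy endpoints and power are unaffected.

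This rests on two assumptions: that the damaged instruction is a best-match instruction, and that the box labels other than the last have been read correctly from the PDF. The sponsor can settle both from the original form.

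**What to change.** Make the stem and boxes of the retching row agree, in one of two ways.

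1. *Counts:* keep the stem and use No, 1–2 times, 3–4 times, 5–6 times, 7 or more times.
2. *Duration:* ask how long the patient retched in total, with contiguous bands, a box for under one hour, and a unit in every box. The nausea bands should not be copied unchanged, since they leave gaps between 1 and 2 hours and between 3 and 4 hours.

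Then define the Section 3.4 measure to match. Option 1 supports banded episode counts per day or days with any retching. Option 2 supports days with any retching, or a measure renamed as duration. State the scoring rule in Section 7.2.

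The cost is one reprinted diary row and a line or two of text. The downside is less direct comparison with diaries already completed on the present form, and with the previous trial's diary if it used the same boxes. Starting the new row only with patients not yet randomized would keep each patient's three periods on one form. Days with any retching could be reported across both forms, noting that the present form may miss short bouts.

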serial seven subtractions. A 12-lead ECG and physical/neurological examination will be conducted. Blood and urine will be obtained for safety analyses. Patients will answer the OH-Questionnaire and be questioned about adverse events. ABPM recordings will be reviewed to determine data quality and will be repeated if not satisfactory. Medication compliance will be checked by asking patients to bring in or email a time stamped photograph of unused pills.. Medications will be dispensed by the Investigational Pharmacy (including those for the titration down and those for the next treatment arm). Prior to starting the next treatment arm, patients will be instructed (in writing [Appendix] and verbally) to titrate down their current dose, by taking one pill in the afternoon of testing and one pill the following day. They will then proceed to a 2-day washout period. After the washout, they will start their next batch of medications three-times per day (q6h). On the day they start their new medications, all patients will receive a phone call to check for adverse events, if concerned, we will bring the patients into the Center for an unscheduled visit. Seven-days after their office visit, patients will be contacted by phone to check for tolerability issues and adverse events. Thereafter, patients will be contacted on a weekly basis and questioned about adverse events. They will also fill a daily symptom diary, which prompts them to note any adverse events.

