4.3 Subject Recruitment and Screening

Since most patient with FD take medications by opening capsules or crushing pills and flushing them through their gastrostomy, it is necessary to use carbidopa powder (rather then re-encapsulate the commercially available pills) to maintain treatment allocation concealment. Subjects randomized to receive placebo will receive an identical small capsule containing a matching powder, as we've previously done. Thirty subjects will be randomized. Randomization will be performed by the Investigational Pharmacy of NYU, and participants, caregivers and assessors will be blinded at all times from the randomization sequence. Randomization sequences will be generated using computer-based system using a permuted block design and the Investigational Pharmacy of NYU will dispense all medications and provide dosing instructions for titration down and washout between treatment arms (Appendix). Investigators will not be involved in specifying the actual doses patients take and will remain blind to treatment allocation throughout. The PI will have the capacity to break the blind and remove any patient from the study at anytime for safety concerns. To monitor compliance, patients will be instructed to return all unused study medications at study visits.

4.3.1 Assessment of mental capacity to consent.

There are few formal assessments of cognitive function in patients with FD. Published studies likely underestimate the frequency of cognitive impairment owing to the bias of only "higher functioning" patients being able to complete the cognitive assessment tests. We estimate that around 40% of patients have impaired cognitive function. Given this we anticipate difficultly completing recruitment goals without enrolling patients with diminished capacity, as this is a rare genetic disease. We have included the following measures to ensure adequate assessment of cognitive impairment and capacity are in place.

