5.9.4 Return or Destruction of Study Drug

At the completion of the study, there will be a final reconciliation of drug shipped, drug consumed, and drug remaining. This reconciliation will be logged on the drug reconciliation form, signed and dated. Any discrepancies noted will be investigated, resolved, and documented prior to return or destruction of unused study drug. Drug destroyed on site will be documented in the study files.

6 Study Procedures

Table 1 provides a complete list of the procedures at each study visit (in the office or via telemedicine 2-way conferencing) and figure 7 provides a timeline for the procedures at visits.

Table 1: Study procedures

Table 1. Study procedures	\/:a:4.4	Violt 0	Visit 3	Visit 4
	Visit 1	Visit 2	VISIT 3	VISIT 4
Procedure	Baseline/R	Crossover 1	Crossover 2	Final
Consent/ascent	Ø			
Urine pregnancy test (reproductive females)	Ø			Ø
Inclusion/exclusion criteria	Ø			
Concomitant medications/compliance check	Ø	Ø	Ø	Ø
Vital signs (temperature, weight)	✓	₫	✓	Ø
Metabolic panel	Ø	Ø	\square	Ø
Urinalysis	v	\square	\square	V
CBC	V	\square	V	\square
12-lead ECG*	V	\square	V	Ø
Physical/neurological examination	v	\square	\square	V
Adverse event questioning	V	\square	V	\square
OH-Questionnaire	Ø	\square	Ø	☑
24-h ambulatory BP recording	Ø	\square	\square	☑
24-h urine catecholamine excretion	V		V	Ø
Supine/seated/standing BP	V		V	Ø
Beat-to-beat BP or HR at rest	V		V	Ø
Beat-to-beat BP during Stroop (Office)	V		V	Ø
HR with serial 7s subtractions (Virtual Visit)	✓	✓	Ø	Ø
Symptom/AE diary collection		\square		\square
Dose de-escalation		Ø	\square	Ø
Washout		Ø	Ø	
Dose adjustment day safety phone call		Ø	Ø	
Day 7 adverse event monitoring phone call	Ø	Ø	Ø	☑

CBC; complete blood count, ECG; electrocardiogram, BP; blood pressure, AE, adverse event; R; randomization.

Visit 1. Baseline/Randomization:

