Did you have anything else that bothered you today (an Adverse Event)?						

Diary Day: 1 of 28

Sample Instructions for Testing/Dose administration:

Dov	Instructions
Day	Instructions
Apr 1st The day before your visit	At 9 AM fit the BP cuff to your < <left>> arm (<<6>> cm above your elbow). Turn the monitor on, start the recording by pressing the blue button, go about your daily activities. Fill in the diary your meal times, times you took medications and the time you go to sleep and wake up. Starting this same morning, discard your first morning urine. For the next 24-h collect your urine in the container provided. Write here when you started the collection. START TIME: AM You should continue to take your study medication every 6-hours.</left>
Apr 2nd The day of your visit	Your appointment or televisit at the Dysautonomia Clinic is scheduled for <<10:00>> AM. Finish your urine collection the same time you started it the previous day. Be sure this time to include your first early morning urine sample after waking up. Write here when you ended the collection: END TIME: AM Take your first morning dose of study medication at <<8:00>> AM. Write down here the exact time you took your medication. MEDICATION TIMING: AM Come into the clinic for your study visit. At 11 AM we will perform your autonomic function tests in the office of via telemedicine. DO NOT take off your BP monitor yet, will take it off when you arrive at the clinic. Here is a check list with things to bring with you to the clinic or have prepared for the televisit: Your symptom diary Your 24-h urine collection The blood pressure monitor (which you should be still wearing) All your unused medication After your visit: So that you do not stop your dose too quickly, we will reduce your current dose slowly. At the end of this visit, we will give you 2 bottles of medication. One bottle will be marked with todays and tomorrows dates, and will contain 2 of the same pills that you have been taking. One bottle will contain more pills. These pills are your next treatment, and you should not start taking them yet. You will take one-pill from the bottle with today and tomorrows date. Once you have taken this pill, do not take any more pills for the rest of the day.
Apr 3rd The day after your visit	IN THE AFTERNOON, TAKE ONE PILL FROM THE BOTTLE MARKED WITH TODAY'S DATE. Do not take any more medication for the rest of the day Apr 2: Take 1 pill Apr 3: Take 1

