Apr 4th Washout No pills	DO NOT TAKE ANY MEDICATION TODAY
Apr 5th Washout No pills	DO NOT TAKE ANY MEDICATION TODAY
Apr 6th Start your new medications today	Start taking your next batch of study pill again, three times a day (every six hours) Morning dose: 8:00 AM Afternoon dose: 2:00 PM Evening dose: 8:00 PM Be sure to keep your diary with your symptoms We will call you in the morning at 10:00 AM to check how you responded to
1000	your first dose of new medication. If you do not feel well, we will ask you to come into the Center.
Apr 7th Continue your three a day schedule	Take your study pills three times daily until May 4th, when you come to the Clinic. Remember to fill your diary
Apr 12th Phone call Safety bloods	We will contact you by phone to check in on how you are feeling. We will arrange for you to have a blood test to check your health status.
May 3rd Day before next visit	Repeat ambulatory monitoring and urine collection. We will send you new instructions with dates and times.
May 4th Next visit # X	Plan to attend your next study visit at the clinic

If you feel unwell at any time, call the Dysautonomia Center at: [contact].

AMBULATORY
MONITORING:
INSTRUCTIONS FOR
PATIENTS

https://dysautonomia.nyumc.org [contact]

You have been asked to wear an ambulatory blood pressure monitor. This will measure your blood pressure for 24-h so that we can better understand of how it changes over a typical day. Some patients may need to wear the monitor for longer.

Step 1: Fitting the cuff

- Place the cuff on your non-dominant arm (the one you don't write with). So it does not restrict movement, it should be on your upper arm, completely above the elbow. The cuff should be tight enough to not fall down, but not uncomfortable. The orange tubing needs to face UP. The word "ART" and arrow should on the inside of your elbow.
- The monitor itself can be worn on a belt or carried in a bag. Make sure you do not drop it.

3.

- Turn the monitor on by flipping the black switch from OFF (O) to ON (I). You should see numbers or letters on the display screen when the monitor is initially on.
- Once the monitor is on press the BLUE button to start the readings.
- The cuff will inflate and start taking your blood pressure

Step 3: Measuring your blood pressure

- The cuff will inflate every 30 minutes to take your blood pressure. The screen may not show your blood pressure readings. The monitor will store your readings in its internal memory.

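### On both washout days the sample dosing sheet's stop order is not limited to study drug, and no line tells patients to continue other permitted medicines (minor safety wording point)

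*Combined protocol and SAP*

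**What the plan says.** The Appendix of the combined protocol and SAP contains a sample sheet of testing and dosing instructions around a crossover visit. It runs from Apr 1 (the day before the visit) to May 4 (the next visit). Apr 4 and Apr 5 are labelled as washout days without pills, and each carries one instruction: "DO NOT TAKE ANY MEDICATION TODAY".

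The two taper days before them also have stop lines. After the visit on Apr 2 the patient reads "Once you have taken this pill, do not take any more pills for the rest of the day", and on Apr 3 "Do not take any more medication for the rest of the day". On Apr 6 dosing resumes: "Start taking your next batch of study pill again, three times a day (every six hours"). No line on the sheet, and none elsewhere in the protocol, tells patients to keep taking their other medicines during taper or washout.

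The protocol body relies on this Appendix. The text under Fig. 6 in section 1.5 says that "patients will be instructed (in writing [Appendix] and verbally) to titrate down their current dose". Section 4.3 says that the Investigational Pharmacy will "provide dosing instructions for titration down and washout between treatment arms (Appendix").

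**The concern.** The two lines are absolute, in capitals, and cover the whole day. Taken at their word, they stop every medicine the patient uses, which the protocol does not ask for.

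That matters because other blood pressure medicines are expected in this population. Section 1.1 names clonidine and benzodiazepines as current treatments. The symptom diary is meant to capture as-needed medicines, and it asks each day whether something was taken for blood pressure or nausea. A patient on clonidine who followed the lines literally would stop it abruptly, and section 1.4 lists rebound hypertension among that drug's unwanted effects.

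The readership adds weight. Section 4.1 admits patients from age 10. Section 4.3.1 estimates that around 40% of patients with familial dysautonomia have impaired cognition and expects to need patients with diminished capacity to reach the recruitment goal. A handout for this group should not depend on the reader inferring its scope.

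**Working it through.** No arithmetic applies. The check is to set the sheet's lines beside each other and beside the protocol body.

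1. **What the word covers on the sheet.** Usage is mixed. The dosing lines on Apr 1, on the morning of Apr 2, on Apr 6 and on Apr 7 specify study drug. Elsewhere the sheet uses the bare word and plainly means study drug: the bottles handed out at the visit, the unused supply to bring back, the dose whose time is to be written down, and the new treatment. The Apr 1 diary line, "Fill in the diary your meal times, times you took medications and the time you go to sleep and wake up", can be read as covering all medicines. The word alone therefore does not settle the scope.

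2. **What the context adds.** The Apr 2 text explains that the current dose is being reduced slowly. The Apr 4 and Apr 5 rows carry the washout label. The Apr 6 line speaks of taking a study pill again, which identifies what had been stopped. Read in sequence, study drug is meant.

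3. **Taper days compared with washout days.** The Apr 2 and Apr 3 stop lines directly follow an instruction about the dated study bottle, which limits their sense. The Apr 4 and Apr 5 lines follow no such instruction and have only the row label.

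4. **Literal reading compared with the protocol.** Section 1.6.2 reduces study medication before washout. Section 1.5 describes a 2-day washout between treatments and mentions no other drug. Sections 4.2 and 5.6 bar MAO-inhibitors, dopamine blockers, tricyclics and neuroleptics; clonidine and benzodiazepines are on neither list. Section 5.6 has all concomitant medicines recorded. Stopping permitted medicines would go beyond anything the protocol requires.

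5. **Efficacy data.** On the sheet, ambulatory recording and urine collection run from the morning of Apr 1 to the Apr 2 visit, before the taper, and are repeated on May 3. Under Visit 2 in section 6, a recording that has to be repeated is made on the same dose before the taper. The washout days lie outside these windows.

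6. **Size.** Two lines are affected. Table 1 marks washout at visits 2 and 3, so a sheet with this wording would be used at two crossovers. The documents do not say how many participants take clonidine, a benzodiazepine or another regular medicine; the range is from none to all 30 (or 36, if enrolment follows section 7.2). Nor do they give a basis for estimating how often the lines would be read literally. No harm rate can be derived.

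**The case against.** The strongest reply is that the sheet supplies its own limits. Its title concerns testing and dose administration, it uses the unqualified word for study drug several times, and the washout rows sit between a taper and a restart of study pills. That stands: the intent is clear, and this is a wording matter.

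It also stands that the sheet is only a sample with fill-in fields, that section 1.5 promises an individualized schedule, and that the issued sheets are not in the documents. Whether any patient received this wording cannot be established.

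The safeguards are real. Instructions are also given verbally, Table 1 has a "Concomitant medications/compliance check" at every visit, the ambulatory monitoring text in section 6 says most patients have home nursing, and the sheet tells patients who feel unwell to call. None of these is said to address the scope of the washout lines. The first scheduled call on the sheet after the visit is on Apr 6, when both washout days are over.

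Three stronger readings are tempting, and the documents do not support them:

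- A reader might infer that, because the sheet specifies study drug on other days, its omission on Apr 4 and Apr 5 signals a wider stop. The mixed usage shown above rules this out. A pill-count fragment in the Apr 3 row also has no qualifier, and the table text is broken there, so counting words across the sheet proves nothing.
- A reader might multiply out the washout days and treat the total as a measure of risk. It is only the planned length of washout.
- A reader might link this to the rebound that section 1.6.2 guards against. That concerns carbidopa withdrawal, which the protocol calls theoretical, and is a separate matter from clonidine.

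**Conclusion.** The point holds as a minor patient-safety wording defect. Two lines of a patient-facing sample omit the limit to study drug, and no line tells patients to continue other permitted medicines. The protocol does not require all medicines to be stopped, and the documents do not show that anyone was harmed or misled.

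The conclusion rests on two assumptions: that some participants take permitted background or as-needed medicines, which the protocol expects but does not count, and that issued sheets may carry over the sample's wording. If the issued sheets already name study drug, the point falls away for them and applies only to the template. There is no consequence for the efficacy recordings or the analysis.

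**What to change.** - On Apr 4 and Apr 5, replace the line with: *Do not take any STUDY medication today; continue your other permitted medicines as usual.*
- For consistency, add the word *study* to the stop lines on Apr 2 and Apr 3.
- Give the same message verbally at each crossover visit, where the concomitant-medication check already provides a natural moment for it.

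The cost is an IRB submission for the reworded handout. No visits or patients are added, and the endpoints and analysis do not change.
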